6.12.1 Data summaries

Summaries on the SAF set by treatment group include:

[figure not shown]
- The proportion of subjects who have completed suicide, suicide attempt, preparatory actions toward imminent suicidal behavior, suicidal ideation, and self-injurious behavior without suicidal intent during the study
- The proportion of subjects with any suicidal behavior engaged in during the study (answered “yes” for any of the C-SSRS suicidal behaviors during the study)
- The proportion of subjects with suicidality (answered “yes” for any of the C-SSRS suicidal behaviors during the study and/or answered “yes” for any of the C-SSRS ideation during the study)

Summaries on the FUS by treatment group will also be presented similarly.

7 Interim analyses

Regular bi-yearly and yearly (starting from the year of 2016) interim analysis for the Data Monitoring Committee (DMC) will be performed by Novartis designated CRO independent statistician and independent statistical programmer. Safety and, if requested by the DMC, efficacy data will be provided. The analysis plan for these safety interim analyses will be provided in a separate document.

Blinded data size re-estimation is also conducted to check the assumptions on ARR and dispersion parameter for power calculation. The interim analysis plan is provided in a separate document.

9 Determination of sample size

9.1 Sample size calculations

The sample size calculations are based on the primary efficacy variable, the annualized relapse rate (ARR). The sample size calculations and power considerations follow the method outlined in Keene et al, 2007 with a constant dispersion parameter k and were programmed manually using the SAS software.

Different scenarios of the anticipated treatment effect between fingolimod versus IFN β -1a, have been evaluated based on the available data on fingolimod and on IFN β -1a in the Phase III program in adults. In the TRANSFORMS study (FTY720D2302), a double-blind, one-year study, fingolimod 0.5 mg was directly compared to interferon beta-1a i.m. The ARR (0.21) in patients treated with fingolimod 0.5 mg was reduced by 52% compared to the ARR (0.43) in patient treated with INF beta-1a.

The initial assumptions for this study (based on adult patient data) was as follows: assuming a 50% relative reduction (from 0.72 to 0.36) in the relapse rate over 24 months (ARR: $\lambda_1=0.18$ for fingolimod, $\lambda_2=0.36$ for interferon beta-1a), a sample size of 95 patients per treatment group (or 190 total) would be needed for a study with a fixed follow-up of 24 months in order to provide 80% statistical power at a two-sided alpha level of 0.05 (with dispersion parameter of $k=0.82$). This corresponds to a statistical information $I=16.36$.

The core phase of the study was amended so that when the information for the blinded data review exceeds the required value of 16.36 (i.e. $I>16.36$) which corresponds to the targeted power for the primary statistical test, all subjects who are ongoing in the core phase will be scheduled for the end of treatment/study visit. Any data collected during follow up but after the core phase data base lock will be reported in the extension phase CSR.

9.2 Power considerations for analysis of key secondary variable

For a 24-month study and assuming a fingolimod rate of n/neT2 lesions over 24 months of 2.3 a sample size of 95 per treatment group (or 190 total) will provide approximately 88% statistical power to detect a relative reduction of 50% (i.e., from 4.6 to 2.3) in the fingolimod group compared to the interferon beta-1a group. This sample size calculation assumes that the number of n/neT2 lesions over 24 months follows a negative binomial distribution. A negative binomial dispersion estimate of 2.0 was assigned which is within the 95% confidence interval. Using the same assumptions as above with a dispersion estimate of 2.67 will provide approximately 79% statistical power to detect a relative reduction of 50% (i.e., from 4.6 to 2.3) in the fingolimod group. These estimates were based on the FREEDOMS study (FTY720D2301).

As illustrated by the above sample size calculations, sample size requirements for the n/ne T2 endpoint to obtain 80% power are lower than those for the primary endpoint. It is therefore assumed that the power for the key secondary endpoint can be maintained at $\geq 80\%$ even if the follow-up duration can be revised based on the results from the blinded data review.

10 Clinical Study Report - Appendix 16.1.9 Documentation of statistical methods

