9.7 Power for analysis of key secondary variables

Core Phase:

For a 24-month study and assuming a fingolimod rate of n/neT2 lesions over 24 months of 2.3 a sample size of 95 per treatment group (or 190 total) will provide approximately 88% statistical power to detect a relative reduction of 50% (i.e., from 4.6 to 2.3) in the fingolimod group compared to the interferon beta-1a group. This sample size calculation assumes that the number of n/neT2 lesions over 24 months follows a negative binomial distribution. A negative binomial dispersion estimate of 2.0 was assigned which is within the 95% confidence interval. Using the same assumptions as above with a dispersion estimate of 2.67 will provide approximately 79% statistical power to detect a relative reduction of 50% (i.e., from 4.6 to 2.3) in the fingolimod group. These estimates were based on the FREEDOMS study (FTY720D2301).

As illustrated by the above sample size calculations, sample size requirements for the n/ne T2 endpoint are lower than those for the primary endpoint. It is therefore assumed that the power for the key secondary endpoint can be maintained at $\geq 80\%$ even if the study duration is revised based on the results from the BSSR.

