4.2.2.2.1 Key secondary analysis

The test of the null hypothesis will be based on a negative binomial regression model adjusted for treatment, number of T2 lesions at baseline, pubertal status (the stratification factor in IVRS), and region. The natural log of time in study for each patient will be used as the offset.

For the key secondary analysis, there will be no imputations for missing data. The response variable for this analysis is the cumulative number of n/neT2 lesions up to Month 24 (i.e., Month 0 to EOS), for each subject. The quadratic variance estimate will be used and the natural log of time (in years) from first dose of study treatment to the last available T2 MRI assessment date for subject will be used as the offset to account for the varying lengths of each subject's time in the study.

The above null hypothesis will be rejected if the observed p-value for treatment comparison (based on the n/neT2 rate ratio) is less than the significance level of 0.05. Model-based estimates (LSmean estimated with the OM option) of the annualized rate of the number of n/neT2 lesions from baseline to end of the core phase, with a duration up to 24 months and their 95% confidence intervals, estimate of the n/neT2 rate ratio (i.e., relative treatment effect) and its 95% confidence intervals and p-value for comparing fingolimod vs. IFN β -1a i.m. will be provided.

The number of n/neT2 relative to baseline and the number of n/neT2 relative to previous visit will also be summarized (mean, standard deviation, median, minimum and maximum) by visit.

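### The claim that n/neT2 needs fewer patients than the primary and keeps at least 80% power under shorter follow-up holds at dispersion 2.0 but fails at the plan's other value, 2.67

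*SAP*

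**What the plan says.** SAP 9.2 and protocol 9.7 carry nearly the same text. Both assume 4.6 n/neT2 lesions over 24 months on interferon and 2.3 on fingolimod, with 95 patients per arm, and give two power figures.

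- About 88%, for which "A negative binomial dispersion estimate of 2.0 was assigned which is within the 95% confidence interval".
- A lower figure: "Using the same assumptions as above with a dispersion estimate of 2.67 will provide approximately 79% statistical power".

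Both sections attribute the estimates to the adult placebo-controlled study D2301. Neither says which dispersion is the point estimate.

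The next paragraph presents its conclusion as following from these calculations. The SAP says "sample size requirements for the n/ne T2 endpoint to obtain 80% power are lower than those for the primary endpoint"; the protocol says "sample size requirements for the n/ne T2 endpoint are lower than those for the primary endpoint". The protocol continues "It is therefore assumed that the power for the key secondary endpoint can be maintained at" 80% or more even if the study duration is revised after the blinded review, and the SAP says the same of follow-up duration.

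For the primary endpoint, SAP 9.1 and protocol 9.6 need 95 per arm for 80% power. SAP 9.1 schedules end-of-study visits "when the information for the blinded data review exceeds the required value of 16.36", which is information on the relapse rate ratio.

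**The concern.** The conclusion has two parts: n/neT2 needs fewer patients than the primary, and its power survives a shorter study. One of the two calculations it rests on gives 79% with the same 95 per arm that gives the primary 80%. At that dispersion n/neT2 needs more patients than the primary, and its power is below 80% at full length.

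n/neT2 is the only hypothesis after the primary in the hierarchical sequence of SAP 4.2.2.1. A reader facing a non-significant n/neT2 result would take the stated power of at least 80% as a property of the design. One of the plan's own two scenarios does not support that, and the statement is made to defend shorter follow-up, where the shortfall grows.

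**Working it through.** **Inputs.** All come from SAP 9.1 and 9.2 (also protocol 9.6 and 9.7), with 1:1 allocation from protocol 5.2.

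- Expected counts over 24 months: primary 0.36 and 0.72; n/neT2 2.3 and 4.6. The rate ratio is 0.5 in both.
- Dispersion k: primary 0.82; n/neT2 2.0 or 2.67.
- Alpha: the key secondary p-value is tested against 0.05 (SAP 4.2.2.2.1: "is less than the significance level of 0.05"). SAP 9.2 does not restate sidedness, so it is taken from SAP 9.1: "statistical power at a two-sided alpha level of 0.05". A one-sided 0.05 test would give 93% and 87%, which do not match the stated figures.

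**Formulas** (protocol Appendix 5, Equation 2)

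- I = n / (1/μ1 + 1/μ2 + 2k), with n per arm
- Power = Φ(ln 2 × √I − 1.960)
- I for 80% = ((1.960 + 0.8416)/ln 2)² = 16.336, so n = 16.336 × (1/μ1 + 1/μ2 + 2k)

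**Plan's figures and required sample sizes, 24 months**

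| Endpoint | 1/μ1 + 1/μ2 + 2k | I at n = 95 | Power | n per arm for 80% |
|---|---|---|---|---|
| Primary, k = 0.82 | 4.167 + 1.64 = 5.807 | 16.36 | 80.06% | 94.9, so 95 |
| n/neT2, k = 2.0 | 0.652 + 4.00 = 4.652 | 20.42 | 87.9% | 76.0, so 76 |
| n/neT2, k = 2.67 | 0.652 + 5.34 = 5.992 | 15.85 | 78.8% | 97.9, so 98 |

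The stated 80%, I = 16.36, 88% and 79% are all reproduced. Using the variance at the pooled mean under the null gives 88.3% and 79.2%, and again 76 and 98 per arm.

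**Break-even dispersion.** With 95 per arm, k = (95/16.336 − 1/μ1 − 1/μ2)/2. This is 2.58 at 24 months, 2.47 at 18 and 2.26 at 12, holding the lesion rate at the adult value. The value 2.67 is above all three.

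**Shorter follow-up** (illustrative lengths, the same for every patient, adult lesion rate, 95 per arm, no dropout or missing scans)

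| Follow-up | k = 2.0 | k = 2.67 |
|---|---|---|
| 24 months | 87.9% | 78.8% |
| 18 months | 86.5% | 77.4% |
| 12 months | 83.5% | 74.6% |

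At 2.0, power stays at or above 80% down to about 8.6 months. Protocol section 4 sets no minimum duration.

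**Unequal follow-up.** A flexible end date spreads follow-up times, which costs a little more. For times uniform on 12–24 months (assumed, mean 18), Equation 1 gives 76.1% at 2.67 and 85.5% at 2.0. Maximum-likelihood information gives 77.2% and 86.3%.

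**Why relapse information is a poor guide to this endpoint.** The dispersion term is 1.64/5.807 = 28% of the variance for the primary but 5.34/5.992 = 89% for n/neT2 at 2.67. More events therefore help the primary much more. At 2.67 with equal follow-up, reaching 80% needs lesion rates 1.37 times the adult value at 24 months, 1.83 times at 18 and 2.74 times at 12. Even an unlimited lesion rate leaves I = 95/5.34 = 17.79, or about 83% power.

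**The case against.** **The gap is small and disclosed.** At 24 months it is 1.2 points of power and 3 patients per arm, and the 79% is printed next to the conclusion. The 2.0 was the assigned value, and retention of power is worded as an assumption. All of this is true and limits the importance of the point. But the assumption is introduced as a consequence of the calculations, and the documents give no reason to set 2.67 aside.

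**The study shortens only if relapse activity is high, and lesion activity may be high too.** This is the strongest objection. The Amendment 7 rationale reports 96% power for the primary at the first blinded review if the study ran its full length. By Equation 2 that is I = 28.7, or relapse rates about 2.5 times those planned if k is still 0.82 (1.8 to 3.2 times for k from 0.5 to 1.0). If lesion rates rose in proportion, power at 2.67 would be about 80–81% at 18 months and 78–80% at 12. If the study stopped exactly when I reached 16.36 with k = 0.82 and equal follow-up, expected relapses per patient would equal the 24-month plan. Proportional lesion counts would then be unchanged, and power would stay at 79–88%. So the figures at the adult lesion rate may be pessimistic. But proportionality is itself an assumption, and the documents give no on-treatment paediatric n/neT2 rate. Protocol 1.1 says only that children tend to have more T2 lesions at the first event. Even with this offset, power at 2.67 is about 78–81%, not reliably above 80%.

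**The planned model adjusts for baseline T2 count.** This could lower the dispersion that applies. The documents do not say whether 2.0 and 2.67 are adjusted values, so it cannot be settled.

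**Part of the stopping text is redacted.** A check on n/neT2 could stand there or in the separate interim analysis plan. The visible rule names only the primary.

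**Conclusion.** The concern holds. The plan's power figures are right; the general conclusion drawn from them is not. At dispersion 2.0 n/neT2 needs 76 per arm and both statements hold for equal follow-up down to about 8.6 months. At 2.67 both fail at the full 24 months: 78.8% power, and 98 per arm against 95 for the primary.

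The 24-month result rests only on the plan's own inputs and formula. The results for shorter follow-up also assume the lengths shown and the adult lesion rate, and a higher paediatric lesion rate would offset some or all of the further loss. The effect is on the stated power and on how a non-significant n/neT2 result would be read. The validity of any test is not affected.

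**What to change.** In SAP 9.2 and protocol 9.7, remove the comparison with the primary and the assumption of at least 80% power. In their place state:

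- With 95 per arm and the adult lesion rates, unadjusted power at 24 months is about 79–88% for dispersion 2.67 to 2.0. At 2.67, 98 per arm would be needed for 80%.
- Shorter follow-up at unchanged lesion rates lowers this, for illustration to 77.4–86.5% at 18 months and 74.6–83.5% at 12 months with equal follow-up, and somewhat further with unequal follow-up. The lengths and the adult rate are assumptions, and a higher lesion rate would work the other way.
- The early stop depends on relapse information and does not guarantee 80% power for n/neT2.

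Limiting the existing sentences to dispersion 2.0 would be the shortest repair of the contradiction, but it would leave the 2.67 case and the effect of follow-up unaddressed. The blinded n/neT2 information could also be reported at the data review, for information only.

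The cost is wording in two places and a less favourable stated power. No patients are added, and no test or stopping rule changes. The protocol edit would formally need an amendment under protocol 11.1. SAP Amendment 2 (August 2017) already postdates the June 2017 target for early end-of-study visits, so the SAP text is the more practical place to make the correction.

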10.1 Statistical methods and analysis outputs

10.1.1 Statistical methods

Statistical Analysis System (SAS) version 9.2 or higher will be used to perform all the statistical analyses in the report.

10.1.1.1 Negative binomial regression model

The primary efficacy variable (aggregate ARR) will be analyzed using a negative binomial regression model adjusted for treatment, region, pubertal status (the stratification factor in IVRS), and number of relapses within the previous 2 years before randomization. Log (time in study in years) is the offset variable. This analysis will be performed on the full analysis set and the per-protocol set. In addition, the negative binomial regression model will be used for several supportive/sensitivity analyses for aggregate ARR excluding patients in the IFN-beta arm who are Nabs-positive at the end of the study, number of new or newly enlarged T2 lesions, number of Gd-T1 lesions. The corresponding negative binomial regression models are specified in Tables 4-1, 4-2 and 4-4.

Below is an example of the SAS codes to perform the negative binomial regression model.

```
*****  
* SAS Codes: Negative binomial regression model  
* Variables in the model:  
* relnum = number of relapses  
* trt = treatment group code  
* reg1a = region code  
* pub=pubertal status  
* n2 = number of relapses within the previous 2 years before randomization  
* sid1a = subject ID  
* lnday = log(days in study/365.25)  
*****;  
proc genmod data=data1;  
  class trt reg1a pub;  
  model relnum=trt reg1a pub n2 / dist=nb  
    link=log  
    offset=lnday maxiter=500;  
  lsmeans trt /cl exp om;  
  estimate 'A - B' trt 1 -1 /exp;  
  ods output estimates=est;
```

```
ods output lsmeans=lst;  
run;
```

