3.1 Analysis sets

All screened subjects (SCR): The SCR set comprises all subjects who were screened. The SCR will be used only for the summary of screening failures.

Randomized set (RAN): The RAN set comprises all subjects who were assigned a randomization number. The RAN will be used for the summaries of subject disposition, protocol deviation, demographic, baseline characteristics, and medical history data.

Full Analysis Set (FAS): The FAS comprises all randomized subjects with assigned treatments who took at least one dose of study medication. Subjects will be analyzed according to the randomized treatment assignment following the intention-to-treat principle,

even if they actually received a different treatment. The FAS will be used for all efficacy analyses.

Safety Set (SAF): The safety set includes all subjects who received at least one dose of study medication. Subjects will be analyzed according to the actual treatment received. The Safety Set will be used for all safety analyses. Subjects will be analyzed according to the treatment they are assigned to at randomization unless a subject takes non-randomized study medications and does not take any study medication as randomized, in that case the subject will be analyzed according to the treatment actually taken.

Per-protocol set (PPS): The PPS is a subset of FAS, consists of all randomized subjects who take at least one dose of study medication and have no major protocol deviations that could confound the interpretation of analyses conducted on the FAS. Major protocol deviations will be determined according to the pre-defined protocol deviation criteria before treatment unblinding. For analyses performed on the PPS, any efficacy data assessed after permanent discontinuation of study medication will be excluded. The PPS will primarily be used for the supportive analyses of the primary efficacy variable and the key secondary variable.

Follow-up set (FUS): The FUS consists of all subjects in the safety set who have at least one visit or who have AE, MS relapse, or concomitant medication starting after study drug discontinuation, but before first dose of the extension study medication (if applicable). Subjects will be grouped in the same way as described above for the analysis on the safety set. Only the safety follow up data analysis will be performed on the follow-up set.

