4.1.2 Time in study for primary analysis

Time in study (days) (i.e., the number of days on study) for each subject will be calculated as the final study phase visit date– 1st core dose date +1.

Final study phase visit date is recorded on the study phase completion eCRF.

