4.2.1.1 Supportive of primary analyses

Supportive analyses will be performed for the primary variable. The FAS will be used unless otherwise specified. All supportive analyses are summarized below and in Table 4-1.

- 1) To assess the impact of study drug discontinuation to the results observed, a supplementary analysis using the same negative binomial model as in the primary analysis will be performed on relapses on study drug (i.e., relapses will be counted only up to study drug discontinuation) in the FAS. The number of days on study drug is calculated as (the last core dose date – 1st core dose date +1).
- 2) A supplementary analysis using the same negative binomial model as in the primary analysis will be performed on all relapses (i.e., confirmed and unconfirmed relapses) in the FAS.
- 3) Analyses on confirmed relapse and on all relapse will be repeated on the PPS.

Table 4-1 Primary efficacy endpoint, primary & supportive/sensitivity analyses

Endpoint	Analysis method	
ARR (confirmed relapses only) (time-based)	Negative binomial model (treatment, region, pubertal status (the stratification factor in IVRS), and number of relapses within the previous two years before randomization) on FAS	Primary analysis
	Negative binomial model (treatment, region, pubertal status (the stratification factor in IVRS), and number of relapses within the previous two years before randomization) excluding data after drug discontinuation on FAS	Supportive analysis
	Negative binomial model (treatment, region, pubertal status (the stratification factor in IVRS), and number of relapses within the previous two years before randomization) on PPS	
ARR (confirmed and unconfirmed relapses) (time-based)	Negative binomial model (treatment, region, pubertal status (the stratification factor in IVRS), and number of relapses within the previous two years before randomization) on FAS	Supportive analysis
	Negative binomial model (treatment, region, pubertal status (the stratification factor in IVRS), and number of relapses within the previous two years before randomization) on PPS	
ARR (confirmed relapses only) (time-based)	Negative binomial model (treatment, region, pubertal status (the stratification factor in IVRS), and number of relapses within the	Sensitivity analysis

	previous two year before randomization) on FAS but exclude patients in the IFN-beta arm who are neutralizing-antibody (Nabs) positive at end of study visit	
--	---	--

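### The per-protocol relapse model stops counting relapses at drug discontinuation but is given time in study as its offset, which biases the rate ratio if off-drug time differs between arms

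*SAP*

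**What the plan says.** - **Relapse count in the PPS.** SAP 3.1: "For analyses performed on the PPS, any efficacy data assessed after permanent discontinuation of study medication will be excluded". Protocol 9.1 has the same rule, and protocol 9.4.4 counts PPS relapses only while on drug.
- **Offset.** SAP 10.1.1.1: "Log (time in study in years) is the offset variable. This analysis will be performed on the full analysis set and the per-protocol set". The example code there has one offset variable, "lnday = log(days in study/365.25"), and no on-drug version.
- **End of time in study.** SAP 4.1.2 counts days from first core dose to the final study phase visit: "Final study phase visit date is recorded on the study phase completion eCRF". It does not stop at the last dose.
- **PPS instruction.** SAP 4.2.1.1 item 3: "Analyses on confirmed relapse and on all relapse will be repeated on the PPS". It names no offset.
- **On-drug analysis in the FAS.** For SAP 4.2.1.1 item 1, "relapses will be counted only up to study drug discontinuation", and the denominator is given beside it: "The number of days on study drug is calculated as" last core dose date minus first core dose date plus 1. This day count appears under no other item.
- **Discontinuers.** SAP 4.2.1.2 and protocol 5.5.9 and 6 keep patients who stop drug in the study, on an abbreviated schedule that runs to Month 24.

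**The concern.** A rate needs a numerator and a denominator that cover the same period. Taken together, SAP 3.1, 4.1.2 and 10.1.1.1 end the PPS relapse count at permanent discontinuation but let the person-time run to the last core visit. Off-drug months then enter as relapse-free months whatever happened in them.

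At stake are the two PPS relapse analyses, on confirmed relapses and on all relapses. They are there to show whether the primary result survives once off-treatment data are set aside. If one arm stops drug more often, the off-drug time distorts the very comparison that was meant to be free of it.

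**Working it through.** **1. Reproduce the plan's own figure.** The documents state no figure for the PPS analysis, so the check starts from the design in protocol 9.6 and SAP 9.1: ARR 0.18 against 0.36, T = 2 years, k = 0.82, 95 patients per group. By protocol Appendix 5, Equation 2:

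I = 95 / (1/0.36 + 1/0.72 + 2 × 0.82) = 95 / 5.807 = 16.36.

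Power = Φ(ln 2 × √16.36 − 1.96) = 80.06%, and the required n is 94.9. All three agree with the plan.

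**2. Do discontinuers stay in the PPS?** SAP Table 3-1 does not list stopping drug as a reason for exclusion. Deviation S03A removes patients with compliance below 80% over the entire study. However, the accountability rate in SAP 3.6.2 divides by the days from first to last dose of dispensed drug, so on that definition stopping early does not by itself lower it. Some stoppers may leave the PPS for other reasons, such as M01 (immunosuppressive medication during double-blind treatment).

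**3. Effect of the mismatch.** Let f be an arm's on-drug share of its time in study. With on-drug relapses over full time in study:

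- observed ARR = true ARR × f
- observed ratio = true ratio × f(fingolimod) / f(IFN)

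If a share p of an arm stops at uniformly distributed times and all stoppers stay to the end, the average stopper is off drug for half the study, so f = 1 − p/2. The values of p are assumptions; the documents give none by arm. The true ratio is 0.50, with ARR 0.18 against 0.36.

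| p fingolimod | p IFN | ARR fingolimod | ARR IFN | Ratio |
|---|---|---|---|---|
| 15% | 15% | 0.167 | 0.333 | 0.500 |
| 5% | 15% | 0.176 | 0.333 | 0.527 |
| 5% | 25% | 0.176 | 0.315 | 0.557 |
| 10% | 30% | 0.171 | 0.306 | 0.559 |
| 25% | 5% | 0.158 | 0.351 | 0.449 |

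Example, fourth row: 0.50 × 0.95 / 0.85 = 0.559. The relapse rates cancel in the ratio, so higher rates than planned would not change the last column.

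**4. Check by model fit.** Negative binomial fits to simulated data (60,000 patients per arm, k = 0.82, 24 months, one data set per scenario) gave, in the same row order:

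- time-in-study offset: 0.506, 0.528, 0.558, 0.551, 0.454
- on-drug offset, same data: 0.506, 0.501, 0.501, 0.494, 0.505

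**5. Scale.** At I = 16.36 the standard error of the log ratio is 1/√16.36 = 0.247. The largest upward shift is ln(0.559/0.50) = 0.11, or 0.45 standard errors. The largest downward shift is ln(0.449/0.50) = −0.11, or 0.44 standard errors.

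**The case against.** The strongest reply is that the PPS offset is under-specified and not wrong. SAP 4.1.1 ties relapses to the matching observation period. SAP 4.1.2 is headed as a definition for the primary analysis. Item 1 of SAP 4.2.1.1 calls its model the same as the primary one and still switches to days on drug, so a shared model does not fix the offset. SAP 4.2.2.2.1 ends the T2 lesion offset at the last available scan, which shortens with the data. The exclusion in SAP 3.1, "any efficacy data assessed after permanent discontinuation of study medication will be excluded", might be stretched to cover person-time. The PPS rows of Table 4-1 prove nothing by their silence, since no row there states an offset.

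The point about Table 4-1 stands, and a matched denominator may well be what the authors intend. But SAP 4.1.1 sends the reader to 4.1.2 for the number of days, time in study comes from a visit date and not from an efficacy assessment, and SAP 10.1.1.1 applies log time in study to the PPS by name. The indirect cues do not override that sentence. At the least, two programmers could follow this SAP to different PPS results.

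Three limits on size also stand:

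- The calculation keeps every stopper in the study. Protocol 6 allows withdrawal when drug is stopped, and if no stopper stayed, f would be 1 and the mismatch would vanish.
- Some stoppers may leave the PPS altogether.
- The shifts are under half a standard error at the planned information.

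A reader might infer that the PPS ratio is biased whatever happens. The documents do not support that: with equal off-drug shares it is unbiased. A reader might also infer that the plan has no sound on-drug estimate. It has one, in item 1 of SAP 4.2.1.1.

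**Conclusion.** The concern holds in a limited form. Followed literally, the SAP pairs on-drug relapses with on-drug plus off-drug time in the PPS. Each arm's PPS ARR is then understated whenever discontinuers with off-drug follow-up remain in that set.

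The ratio is affected only if the off-drug share of study time differs between arms. More stopping on IFN pulls it toward 1; more stopping on fingolimod exaggerates the benefit. For a true ratio of 0.50 the range is about 0.45 to 0.56, assuming discontinuation of 5% to 30%, uniform stop times and stoppers who stay in the study.

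One might be tempted to carry this over to the primary result, but the documents do not support that. The primary analysis counts relapses on and off drug over full time in study and is consistent, as is the FAS on-drug analysis. The hierarchical test in SAP 4.2.2.1 does not include the PPS. What is affected is the two supportive PPS relapse analyses. They should be corrected before unblinding, because the choice of offset can move the result either way.

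**What to change.** In SAP 4.2.1.1 item 3, the PPS rows of Table 4-1 and SAP 10.1.1.1:

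- State that, for PPS relapse analyses, the offset for a patient who permanently discontinued is ln((last core dose date − first core dose date + 1)/365.25).
- State that only relapses starting within that interval are counted, for both the confirmed-relapse and the all-relapse analysis.
- Keep time in study as the offset for the FAS analyses that count relapses on and off drug.

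The cost is a few sentences of SAP text and the use of a variable already derived for item 1. No new data are needed and the primary analysis does not change.
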